8.2.2 Time to discontinuation of LCM

Time to discontinuation of LCM from the date of first dose of LCM will be analyzed using Kaplan-Meier methods for the SS, the FAS and the modified FAS. The median time to discontinuation (days) of LCM including corresponding 2-sided 95% CIs for the median time to discontinuation will be calculated. Patients who complete the 6-month Observation Period will be censored on the date of the final LCM administration or the study termination date if the date of the final LCM administration is not available.

Supportive Kaplan-Meier plots of time to discontinuation of LCM from the date of first dose of LCM will be presented for the SS, the FAS and the modified FAS.

8.2.3 EQ-5D-5L

Descriptive statistics for the observed value and change from Visit 1 (Baseline) to Visit 3 (Month 6 or end of Observation Period) in the EQ-5D-5L VAS score and utility as converted from the 5 dimensions using the most recent value set will be presented. The EQ-5D-5L will be assessed only for patients with an evaluable Baseline assessment (eg, patients who have not started LCM at the time of the Visit 1 assessment).

8.2.4 M.D. Anderson Symptom Inventory Brain Tumor Module

Descriptive statistics for the observed value and change from Visit 1 (Baseline) to Visit 3 (Month 6 or end of Observation Period) in the individual items of the MDASI-BT, the mean core symptom severity scale, the mean module symptom severity, the mean total symptom severity and mean interference will be presented. The MDASI-BT will be assessed only for patients with an evaluable Baseline assessment (eg, patients who have not started LCM at the time of the Visit 1 assessment).

8.2.5 Seizure frequency

Descriptive statistics for absolute values and percent change from Baseline will be presented by visit for the following variables:

- Partial-onset seizure frequency per 28 days for focal seizures with and without secondary generalization
- Partial-onset seizure frequency per 28 days for focal seizures without secondary generalization.
- Partial-onset seizure frequency per 28 days for focal seizures with secondary generalization
- Partial-onset seizure frequency per 28 days that occurred at less than 200 mg/day

The Baseline for all subjects in the FAS and the Baseline for subjects who received at least one dose of <200mg/day LCM during the treatment period will be summarized for Visit 1 which only includes subjects who have a dose of <200mg/day at some point during the study and thus would have a seizure frequency at <200mg/day LCM reported. Percentages are based on the number of patients with available data.

8.2.6 Seizure-free status

The number and percentage of patients achieving a seizure-free status (Yes/No) at the end of the 6-month Observation Period will be presented. Percentages are based on the number of patients with available data. A 2-sided 95% CI (calculated using the 2-sided Clopper-Pearson method) for the percentage of patients achieving a seizure-free status (Yes/No) will be presented.

8.2.7 Discontinuation of LCM due to an ADR

The number and percentage of patients who discontinue LCM due to an ADR will be presented for the SS, the FAS and the modified FAS. A 2-sided 95% CI (calculated using the 2-sided Clopper-Pearson method) for the percentage of patients who discontinue LCM due to an ADR will be presented.

8.2.8 Discontinuation of LCM due to lack of efficacy

The number and percentage of patients who discontinue LCM due to lack of efficacy will be presented for the SS, the FAS and the modified FAS. A 2-sided 95% CI (calculated using the 2-sided Clopper-Pearson method) for the percentage of patients who discontinue LCM due to lack of efficacy will be presented.

8.2.9 Discontinuation of LCM due to lack of effectiveness

The number and percentage of patients who discontinue LCM due to lack of effectiveness will be presented for the SS, the FAS and the modified FAS. A 2-sided 95% CI (calculated using the 2-sided Clopper-Pearson method) for the percentage of patients who discontinue LCM due to lack of effectiveness will be presented.

8.2.10 Clinical Global Impression of Change

The number and percentage of patients within each response category for CGIC (1=very much improved, 2=much improved, 3=minimally improved, 4=no change, 5=minimally worse, 6=much worse, and 7=very much worse) will be summarized for the FAS and modified FAS.

Additionally, the number and percentage of patients who improved (impression of change <4), had no change (impression of change =4), and worsened (impression of change >4) will also be provided.

Percentages are based on the number of patients with available data.

9 PHARMACOKINETIC AND PHARMACODYNAMICS

Not applicable.

10 SAFETY ANALYSES

All statistical analyses for the safety variables will be performed for the SS and the modified FAS in an exploratory manner. Exposure data will be listed in the SS and adverse drug reactions will be listed in the ES.

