3.5.3 Full Analysis Set

The Full Analysis Set (FAS) is defined as all patients in the SS who have at least 1 post-Baseline PGIC or seizure assessment. The FAS will be used for the analysis of the primary and most secondary variables including any subgroup analyses. In addition, demographic and baseline summaries will be based on the FAS.

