3.5.4 Modified FAS

The modified FAS is defined as all patients in the FAS ≥ 16 years of age and treated with daily LCM doses ≤ 400 mg, representing the on-label use of LCM. All efficacy analyses excluding subgroup analyses, demographic and baseline summaries and some safety summaries will be repeated in the modified FAS.

On-label use for this study is defined as receiving a LCM daily dose ≤ 400 mg. Patients who receive at least one dose of LCM that is >400 mg will be excluded from the modified FAS.

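### SAP 10 shows on-label safety in the modified FAS, whose inherited efficacy-assessment condition drops on-label patients who leave before any post-Baseline assessment

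*SAP*

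**What the plan says.** SAP 10 sets the populations for safety: "All statistical analyses for the safety variables will be performed for the SS and the modified FAS in an exploratory manner". It also lists exposure in the Safety Set (SS) and ADRs in the Enrolled Set (ES).

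The populations are nested:

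- SAP 3.5.2: the SS is everyone who took lacosamide (LCM) at least once in the study.
- SAP 3.5.3: the FAS is "all patients in the SS who have at least 1 post-Baseline PGIC or seizure assessment".
- SAP 3.5.4: "The modified FAS is defined as all patients in the FAS" who are 16 or older and whose daily dose is 400 mg or less. It adds: "Patients who receive at least one dose of LCM that is >400 mg will be excluded from the modified FAS".

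The same section gives the meaning of the label: "On-label use for this study is defined as receiving a LCM daily dose" of at most 400 mg. No assessment condition appears in that definition.

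On scope, SAP 3.5.4 says that "demographic and baseline summaries and some safety summaries will be repeated in the modified FAS", whereas SAP 10 puts every safety analysis there.

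SAP 8.2.7 reads: "The number and percentage of patients who discontinue LCM due to an ADR will be presented for the SS, the FAS and the modified FAS". SAP 8.2.1, 8.2.2, 8.2.8 and 8.2.9 use the same three sets. Protocol 11.1 assigns safety data, retention, discontinuation rates and time to discontinuation to the SS, and SAP 3.9 records no change from the protocol's analyses.

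**The concern.** An efficacy-evaluability condition has been carried into safety tables that are meant to describe on-label use. It plays no part in the SAP's own definition of on-label. It enters only because the on-label set was built from an efficacy population, and no on-label set is drawn from the SS.

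The patients it removes are those who leave before any post-Baseline assessment. Stopping early because of an ADR is one way to become such a patient; dying early is another. If these patients have ADRs, serious ADRs, fatal outcomes or ADR-related discontinuation more often than the rest, the on-label rates come out too low.

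There is also a problem of reading. The SAP 10 tables show the SS and the modified FAS but not the FAS. A difference between them may come from doses above 400 mg, from missing assessments, or from both.

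**Working it through.** **1. The plan's own figure.** Inputs from Protocol 11.5 and SAP 2.4: expected responder rate 0.60, half-width 0.10, two-sided 95%, normal approximation.

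- n = 1.96² × 0.60 × 0.40 / 0.10² = 92.2, rounded up to 93.
- Half-width at 93 = 1.96 × √(0.24/93) = 0.0996.
- The step from 93 to 100 implies a 7% loss: 93 / (1 − 0.07) = 100.

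The figure reproduces. It is a precision target for the Visit 3 responder rate. It does not predict the size of the FAS.

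**2. Who is dropped.** By definition, modified FAS ⊂ FAS ⊂ SS. Protocol Table 15-1 schedules PGIC at Visit 3 only, and post-Baseline seizure information at Visits 2 and 3 only (about 3 and 6 months). Early leavers are asked to do the Visit 3 assessments as a Withdrawal Visit, but this is a recommendation. SAP 3.2.2 provides for patients with no Visit 3, death included. A patient who leaves before Visit 2 with no Withdrawal Visit assessment is in the SS and in neither the FAS nor the modified FAS, whatever the dose. A single seizure count at Visit 2 or at a Withdrawal Visit keeps the patient in.

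**3. Whether the safety data exist.** They can. Protocol 10.1.7 has ADRs reported within 1 working day and later extracted from the global safety database. Protocol 8.2 requires the primary reason for withdrawal to be recorded. SAP 3.10.10 derives discontinuation due to an ADR from that reason. None of this needs a PGIC or a seizure count.

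**4. Illustration.** Assumptions: all 100 enrolled patients are treated, all within the dose limit; the 7 non-evaluable patients (100 − 93) are those with no assessment; m patients stop for an ADR, of whom k are among the 7. An on-label set drawn from the SS gives m/100. The modified FAS gives (m − k)/93.

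| m (rate from SS) | k | modified FAS |
|---|---|---|
| 10 (10.0%) | 0 | 10/93 = 10.8% |
| 10 | 1 | 9/93 = 9.7% |
| 10 | 3 | 7/93 = 7.5% |
| 10 | 7 | 3/93 = 3.2% |
| 20 (20.0%) | 0 | 20/93 = 21.5% |
| 20 | 4 | 16/93 = 17.2% |
| 20 | 7 | 13/93 = 14.0% |

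The modified FAS rate is too low when (m − k)/93 < m/100. This rearranges to 100k > 7m, or k/7 > m/100: the event rate among the dropped patients must exceed the overall rate. With m = 10 this needs k > 0.7, so one patient is enough. With m = 20 it needs k > 1.4, so two. With k = 0 the rate is slightly too high, because only the denominator shrinks.

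**5. Where the two conditions can be separated.** In SAP 8.2.1, 8.2.2 and 8.2.7 to 8.2.9 the SS, FAS and modified FAS appear together. SS against FAS shows the assessment condition. FAS against modified FAS shows the dose condition, since the age condition repeats Selection Criterion 4. The SAP 10 tables have no FAS version, so there the two remain mixed.

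**The case against.** The strongest reply is that no safety information is lost. Every safety analysis is run on the SS, ADRs are listed on the ES, and the modified FAS tables are a repeat in a descriptive study. SAP 5.1 reports the size of all four sets and lists each patient's membership, so the number excluded by each condition can be seen. All of this stands. A reader might infer that early ADR stoppers vanish from the report; they do not. They are missing only from the on-label version.

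A reader might also infer that the on-label rates are biased downward. The documents do not support that as a fact. The illustration runs to both sides of 10.0%, and the Withdrawal Visit may keep many early stoppers in.

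Nor are the 7 patients shown to be FAS exclusions. The term evaluable is not defined, the 93 relates to the Visit 3 responder rate, and FAS entry is easier because a Visit 2 seizure count is enough. Some of the 7 might never be treated and so would be outside the SS as well. The real loss may be smaller.

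The illustration has a further limit. If everyone is on label, the SS is itself the on-label set and prints the right figure alongside. The modified FAS figure misleads most when some patients exceed 400 mg and some unassessed patients have events. The documents quantify neither.

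It would also be too strong to say that the set differences cannot be interpreted at all, because the FAS results separate the two conditions for retention and discontinuation. SAP 10.2 also tabulates ADRs by dose at onset, which is a partial substitute but gives no rate per on-label patient.

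What remains is that the set labelled on-label carries a condition unrelated to the label, and no other set gives a patient-level on-label ADR rate.

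**Conclusion.** The point holds as a defect in how the on-label safety population is built. It follows from the definitions in SAP 3.5.3, 3.5.4 and 10 and needs no assumption. Its size does need assumptions. With all 100 treated on label, 10 stopping for an ADR and the 7 non-evaluable patients equated with those lacking an assessment, 10.0% would be shown as anything from 3.2% to 10.8%. The number affected and the direction are not known from the documents.

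The effect is confined to the modified FAS safety tables and to the FAS and modified FAS versions of retention, time to discontinuation and the discontinuation rates. The SS results and ES listings are complete. The mixing of dose and assessment conditions is a problem only in the SAP 10 tables. The change should be made, but nothing here undermines the overall safety result.

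Two textual matters go with it. SAP 3.5.4 and SAP 10 disagree on whether some or all safety summaries are repeated in the modified FAS. The use of sets beyond the SS for safety and discontinuation departs from Protocol 11.1 without being recorded in SAP 3.9.

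**What to change.** - In SAP 3.5, define an on-label Safety Set: SS patients who meet the SAP's existing age and dose conditions, with no assessment requirement.
- Use it in place of the modified FAS for all SAP 10 summaries (exposure and ADR tables).
- Add it as the on-label set in SAP 8.2.1, 8.2.2 and 8.2.7 to 8.2.9. Keep the SS, FAS and modified FAS results there, because together they separate the dose and assessment conditions.
- Leave the modified FAS in place for the seizure, PGIC, CGIC, EQ-5D-5L and MDASI-BT outcomes.
- Reconcile SAP 3.5.4 with SAP 10 on which safety summaries are shown for on-label use, and record the departure from Protocol 11.1 in SAP 3.9.

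The cost is one population flag, some extra tables and a few lines of SAP text. No new data are needed. The on-label ADR figures may look slightly less favourable.

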10.1 Extent of exposure

The following information about intake of LCM during the study will be summarized:

- Duration of exposure (days) including patient years of exposure
- Maximum daily dose (mg/day)
- Modal daily dose (mg/day)
- LCM ongoing at the end of the study (yes, no)

10.2 Adverse events

Adverse drug reactions will be coded for analysis with version 16.1 of MedDRA. Note that AESIs will be collected as ADRs and consequently AESIs will be included in the summary tables and listings for ADRs.

Adverse drug reactions that occur during this study will be presented by MedDRA SOC and PT in a frequency table giving the number and percentage of patients experiencing each event at least once as well as the number of events. For the number and percentage of patients, patients

with multiple ADRs will be counted only once within each PT and SOC. All table summaries will be sorted alphabetically by SOC and by decreasing relative frequency of each PT within SOC.

The following tabular summaries will be presented.

- Adverse drug reactions
- Serious ADRs
- Non-serious ADRs
- Non-serious ADRs above reporting threshold of 5% (as per the requirements for the EU agency)
- Adverse drug reactions leading to discontinuation
- Deaths
- ADRs by dose at onset (dose categories will be agreed during the DEM to obtain a sensible distribution)
- Other significant ADRs

An overall summary table of all ADRs will be presented summarizing the ADR categories given above (except non-serious ADRs above reporting threshold).

A listing of all ADRs will be provided as follows:

- Individual patients (identified by patient numbers) experiencing a given ADR grouped by SOC, High Level Term (HLT), PT, and severity.
- A glossary of all physician-reported terms, grouped by coded SOC, HLT, and PT. This table will serve as a glossary of PTs, showing which reported terms are summarized under each PT.

11 OTHER ANALYSES

Not applicable.

12 REFERENCES

Not applicable.

This document cannot be used to support any marketing authorization application and any extensions or variations thereof.
REDACTED COPY

13 APPENDICES

13.1 Other Significant ADRs

The following preferred terms will be used to define other significant ADRs:

REDACTED COPY

This document cannot be used to support any marketing authorization application and any extensions or variations thereof.

Table 13–1: Preferred terms of other significant ADRs

MedDRA Preferred Term
Hepatotoxicity related terms
Hepatitis toxic
Hepatotoxicity
Cardiac and ECG Related Terms
Atrioventricular block third degree
Atrioventricular block second degree
Bradyarrhythmia*
Bradycardia*
Cardiac pacemaker insertion
Atrial fibrillation
Atrial flutter
Sinus bradycardia*
Ventricular tachycardia
Ventricular fibrillation
Heart Rate decreased*
Sick sinus syndrome
Suicidality related terms
Completed suicide
Depression suicidal
Suicidal behaviour
Suicidal ideation
Suicide attempt

This document cannot be used to support any marketing authorization application and any extensions or variations thereof.
REDACTED COPY

Intentional self-injury
Self injurious behaviour
Self-injurious ideation
Intentional overdose
Multiple drug overdose intentional
Poisoning deliberate
Additional terms
Loss of consciousness
Syncope

*All cases with reported reduced heart rate will be reviewed and only cases with marked bradycardia (marked reduction in heart rate) with HR <45 bpm will be listed as 'Other Significant AEs'.

This document cannot be used to support any marketing authorization application and any extensions or variations thereof.
REDACTED COPY

14 AMENDMENT(S) TO THE STATISTICAL ANALYSIS PLAN (SAP)

14.1 AMENDMENT 1

Rationale for the amendment

The observational study plan was amended on 1 June 2015. These changes were incorporated into the SAP. In addition, during the course of the study clarification was added to the SAP where required. The clarifications are also reflected in this SAP amendment. Other significant ADRs were also added along with clarification of seizure frequency and safety analyses for patients who take at least 1 dose of LCM that is <200mg/day. In addition, the modified FAS definition was updated to reflect the changes in the label where patients are allowed to received LCM as a monotherapy.

Modifications and changes

Change 1 - Study title

A NONINTERVENTIONAL STUDY OF VIMPAT® (LACOSAMIDE) ADDED TO ONE BASELINE ANTIEPILEPTIC DRUG THERAPY IN PATIENTS WITH BRAIN TUMOR RELATED EPILEPSY (VIBES)

Has been changed to:

A NONINTERVENTIONAL STUDY OF VIMPAT® (LACOSAMIDE) AS ADJUNCTIVE ANTIEPILEPTIC DRUG THERAPY IN PATIENTS WITH BRAIN TUMOR RELATED EPILEPSY (VIBES)

Change 2 - Abbreviations

LOCF Last observation carried forward

Has been removed.

Change 3 – 1 Introduction

This document outlines the planned analyses to support the EP0045 clinical study report (CSR). It includes all definitions and details for the evaluation of data recorded during the study. This SAP should be read in conjunction with the non-interventional study observation plan dated 23 June 2014 and the annotated case report forms (aCRF) dated 23 September 2014.

Has been changed to:

This document outlines the planned analyses to support the EP0045 clinical study report (CSR). It includes all definitions and details for the evaluation of data recorded during the study. This SAP should be read in conjunction with the non-interventional study observation plan dated **1 June 2015** and the annotated case report forms (aCRF) dated **31 August 2017**.

Change 4 – 2.1.1 Primary objective

The primary objective of this study is to evaluate the effectiveness and patient global impression of lacosamide (LCM) added to a single antiepileptic drug (AED) in the treatment of patients with brain tumor-related epilepsy (BTRE) due to low-grade primary brain tumor.

Has been changed to:

The primary objective of this study is to evaluate the effectiveness and patient global impression of lacosamide (LCM) added to **1 or 2** antiepileptic drugs (AEDs) in the treatment of patients with brain tumor-related epilepsy (BTRE) due to low-grade primary brain tumor.

Change 5 – 2.1.2 Secondary objective

The secondary objective of this study is to evaluate the tolerability and quality of life (QoL) of patients with BTRE due to low-grade primary brain tumor who are treated with LCM added to a single AED.

Has been changed to:

The secondary objective of this study is to evaluate the tolerability and quality of life (QoL) of patients with BTRE due to low-grade primary brain tumor who are treated with LCM added to **1 or 2** AEDs.

Change 6 – 2.3 Study design and conduct

EP0045 is a multicenter, prospective, single-arm non-interventional study (NIS) conducted at specialized sites utilizing LCM added to AED monotherapy in patients ≥ 16 years of age with BTRE secondary to low-grade tumor.

Has been changed to:

EP0045 is a multicenter, prospective, single-arm non-interventional study (NIS) conducted at specialized sites utilizing LCM added to **existing treatment with 1 or 2 AEDs** in patients ≥ 16 years of age with BTRE secondary to low-grade tumor.

Change 7 – 2.3 Study design and conduct

These visits will consist of:

- Visit 1, Baseline (to be performed before the first dose of LCM)
- Visit 2, approximately 3 months after Baseline according to routine practice
- Visit 3, approximately 6 months after Baseline according to routine practice or end of Observation Period

Has been changed to:

These visits will consist of:

- Visit 1, Baseline
- Visit 2, approximately 3 months after Baseline according to routine practice
- Visit 3, approximately 6 months after Baseline according to routine practice or end of Observation Period

Change 8 – 3.2.1 Analysis time points

- Visit 1, Baseline (prior to first dose of LCM)
- Visit 2 (approximately 3 months after Baseline)

- Visit 3 (approximately 6 months after Baseline or Withdrawal Visit for patients who discontinue early)

Has been changed to:

- Visit 1, Baseline
- Visit 2 (approximately 3 months after Baseline): **Visits that occurred \leq 135 days after Visit 1**
- Visit 3 (approximately 6 months after Baseline or Withdrawal Visit for patients who discontinue early): **All visits that occurred $>$ 135 days after Visit 1**

If there are 2 visits that meet the criteria for Visit 2, then the visit nearest to the scheduled assessment time for Visit 2 will be used (i.e. 90 days after Visit 1). If there are 2 visits that meet the criteria for Visit 3, then the visit nearest to the scheduled assessment time for Visit 3 will be used (i.e. 180 days after Visit 1).

Change 9 – 3.5.3 Full Analysis Set

The Full Analysis Set (FAS) is defined as all patients in the SS who have at least 1 post-Baseline PGIC or seizure assessment. The FAS will be used for the analysis of the primary and most secondary variables.

Has been changed to:

The Full Analysis Set (FAS) is defined as all patients in the SS who have at least 1 post-Baseline PGIC or seizure assessment. The FAS will be used for the analysis of the primary and most secondary variables **including any subgroup analyses. In addition, demographic and baseline summaries will be based on the FAS.**

Change 10 – 3.5.4 Modified FAS

The modified FAS is defined as all patients in the FAS \geq 16 years of age and treated with daily LCM doses \leq 400mg, representing the on-label use of LCM. All efficacy analyses, demographic and baseline summaries and some safety summaries will be repeated in the modified FAS.

On-label use for this study is defined as not receiving a LCM dose of $>$ 400mg and continuing to receive one core AED. Patients who receive at least one dose of LCM that is $>$ 400mg or whose dosage of the core AED changes to 0mg (i.e. patient starts to receive LCM as monotherapy) will be excluded from the modified FAS.

Has been changed to:

The modified FAS is defined as all patients in the FAS \geq 16 years of age and treated with daily LCM doses \leq 400mg, representing the on-label use of LCM. All efficacy analyses **excluding subgroup analyses**, demographic and baseline summaries and some safety summaries will be repeated in the modified FAS.

On-label use for this study is defined as receiving a LCM daily dose \leq 400mg. Patients who receive at least one dose of LCM that is $>$ 400mg will be excluded from the modified FAS.

Change 11 – 3.6 Treatment assignment and treatment groups

All patients treated received LCM with the dosage determined at the discretion of the physician. Data summaries will be presented based on the total number of patients and will not be differentiated by LCM dose with the exception of the frequency of seizures occurring at doses of LCM < 200 mg. Where appropriate, LCM dose will be presented on patient data listings.

Has been changed to:

All patients treated received LCM with the dosage determined at the discretion of the physician. Data summaries will be presented based on the total number of patients and will not be differentiated by LCM dose with the exception of the frequency of seizures occurring at doses of LCM < 200 mg **and ADRs presented by dose**. Where appropriate, LCM dose will be presented on patient data listings.

Change 12 – 3.10.4 Seizure Frequency

The considered time interval is defined as 56 days for the historical seizure count at Baseline (8 weeks x 7 days) and as date of actual visit – date of previous visit for all other time points.

Has been changed to:

The considered time interval is defined as 56 days for the historical seizure count at Baseline (8 weeks x 7 days) and as date of actual visit – date of previous visit for all other time points. **Note if any subjects have a diagnosis of epilepsy less than 8 weeks prior to study entry, then site will be instructed to give their best approximation of the 8-week seizure frequency and the reported historical seizure count will be assumed to be representative of the full 8 weeks. The seizure frequency per 28 days cannot be derived using the time from diagnosis of epilepsy to study start as the time period for reporting the historical seizure frequency for such subjects because only the month and year are collected for the date of diagnosis.**

Change 13 – 3.10.4 Seizure Frequency

Similarly, the frequency of partial-onset seizures observed at a dose less than 200 mg/day will also be calculated based upon the response to the question 'Number of partial-onset seizures that occurred at a lacosamide dose less than 200 mg/day' in the CRF. If the number at less than 200 mg/day is not applicable, then the number of partial-onset seizures at less than 200 mg/day is 0 otherwise it will be taken from the CRF.

Has been changed to:

Partial-onset seizure frequency per 28 days at a dose of <200mg/day at Visit 2 and Visit 3 will be derived from the number of days in the considered time interval (D) for which seizure information was provided where the subject was on a dose of <200mg/day according the dosing log for LCM:

(Number of seizures over the specified time interval) x (28/D).

The number of seizures is the number of partial onset seizures at a dose <200mg/day. The time interval for Visit 2 is the number of days between the Visit 1 and Visit 2 dates where the subject was on a dose <200mg/day for LCM. The time interval for Visit 3 is the number of days between the Visit 2 and Visit 3 dates where the subject was on a dose <200mg/day for LCM. The change from baseline will then be derived by subtracting the partial onset seizure frequency per 28 days reported at Baseline from the partial onset seizure frequency per 28 days on a dose <200mg/day at Visit 2 and Visit 3. If the number at less than 200

mg/day is not applicable, then the number of partial-onset seizures at less than 200 mg/day is treated as missing.

Change 14 – 3.10.6 Retention rate

The 6-month retention rate is the percentage of patients remaining in the study and on LCM treatment for 6 months. This will be estimated using Kaplan-Meier methodology applied to the time to discontinuation of LCM. The derivation of the time to discontinuation and the corresponding censoring flag are described in Section 3.10.7.

Has been changed to:

The 6-month retention rate is the percentage of patients remaining in the study and on LCM treatment for 6 months. This will be estimated using Kaplan-Meier methodology applied to the time to discontinuation of LCM. **A cut of 180 days will be used for 6 months.** The derivation of the time to discontinuation and the corresponding censoring flag are described in Section 3.10.7.

Change 15 – 3.10.7 Time to discontinuation of LCM

Time to discontinuation of LCM will be defined as

The date of last administration of LCM while in the study - the date of first dose of LCM + 1

If the date of last administration of LCM while in the study is not available the study termination date will be used. If the start date of LCM is missing, then it is assumed that the patient did not receive treatment and they would be consequently excluded from the relevant analysis sets and therefore from this analysis.

A censor flag will be derived where patients who remain on treatment at the end of the 6-month Observation Period are censored and patients who have discontinued LCM prior to the end of the 6-month Observation Period are not censored.

Has been changed to:

Time to discontinuation of LCM will be defined as

The date of last administration of LCM while in the study - the date of first dose of LCM + 1

If the date of last administration of LCM while in the study is not available the study termination date will be used. If the start date of LCM is missing, then it is assumed that the patient did not receive treatment and they would be consequently excluded from the relevant analysis sets and therefore from this analysis.

A censor flag will be derived where patients who **completed the study** are censored and patients who have discontinued LCM prior to the end of the 6-month Observation Period (**early withdrawals**) are not censored.

Change 16 – 3.10.9 M.D. Anderson Symptom Inventory Brain Tumor Module

The symptom severity scale is the mean of the 13 symptom items. If at least 7 of the items have been scored, then the symptom severity scale is the sum of the items answered multiplied by 13 and divided by the number of items answered.

The overall symptom distress is the mean of the 6 interference items. If more than 50% of the items are answered, then the overall symptom distress is the sum of the items answered multiplied by 6 and divided by the number of items answered.

Absolute scores and changes from Visit 1 (Baseline) to Visit 3 (Month 6 or end of Observational Period) for the individual items of the MDASI-BT, the symptom severity scale and the overall symptom distress will be derived for patients with an evaluable Baseline assessment. Patients with an evaluable Baseline assessment for MDASI-BT are defined as patients who have not started LCM at the time of Visit 1.

Has been changed to:

The **mean core symptom severity** is the mean of the 13 **core symptom items**. If at least 7 of the items have been scored, then the **mean core symptom severity** is the sum of the items answered divided by the number of items answered.

The mean module symptom severity is the mean of the 9 brain tumor specific symptom items. If at least 5 of the items have been scored, then the mean module symptom severity is the sum of the items answered divided by the number of items answered.

The mean total symptom severity is the mean of all 22 symptom items. If more than 50% of the items are answered, then the mean total symptom severity is the sum of the items answered divided by the number of items answered.

The **mean interference** is the mean of the 6 interference items. If more than 50% of the items are answered, then the **mean interference** is the sum of the items answered divided by the number of items answered.

Absolute scores and changes from Visit 1 (Baseline) to Visit 3 (Month 6 or end of Observational Period) for the individual items of the MDASI-BT, **the mean core symptom severity scale, the mean module symptom severity, the mean total symptom severity and mean interference** will be derived for patients with an evaluable Baseline assessment. Patients with an evaluable Baseline assessment for MDASI-BT are defined as patients who have not started LCM at the time of Visit 1.

Change 17 – 3.10.11 Discontinuation of LCM due to lack of efficacy

The following text has been added:

